# 3.3.7 Monitoring

- 3.3.7.1 Patients may be observed in the hospital for administration of cycle 1 Days 1 and 2 of therapy (at the discretion of the investigator).
- 3.3.7.2 Routine labs (cbc w/differential, acute care, mineral, hepatic panels, uric acid and LDH) will be performed on Day 1, 2, 8, 15, and 22 of cycle 1 and Day 1 of each cycle during cycles 2-8 and on Day 1 (or within 7 days prior to day 1) of every third cycle during extension phases I and II.
- 3.3.7.3 Myeloma tests include serum protein electrophoresis, serum immunofixation, serum free light chains, quantitative immunoglobulins, beta-2 microglobulin and will be performed at baseline and Day 1 of each cycle and on Day 1 (or within 7 days prior to day 1) of every third cycle during extension phase I and II. Subsequent serum immunofixation will only be performed on those patients clinically indicated.
- 3.3.7.4 Random urine sample for protein electrophoresis (UPEP) and immunofixation to assess for monoclonal protein in the urine (Bence-Jones proteinuria) to be performed at baseline, day 1 of each cycle 1-8, and day 1(or within 7 days prior to day 1) of every third cycle during extension phase I and II. In patients whose measurable disease is best determined by measuring Bence- Jones protein quantification, a 24-hour UPEP will be performed at baseline, day 1 of each cycle 1-8, and day 1 (or within 7 days prior to day 1) of every third cycle during extension phase I and II. Otherwise, 24-hr UPEP Bence-Jones quantification will be estimated from random UPEP specimens performed at baseline, day 1 of each cycle 1-8, and day 1 (or within 7 days prior to day 1) of every third cycle during extension phase [46].
- 3.3.7.5 Patients will have clinic visits with H&P or standard progress notes assessing for toxicity/side effects on Day 1, 2, 8, 15, and 22 of cycle 1 and Day 1 (or within 7 days prior to day 1) of each cycle during cycles 2-8 and on Day 1 (or within 7 days prior to day 1) of every third cycle during extension phases I and II. May be delayed up to 7 days per PI discretion for clinical or logistical reasons.

Version Date: 01/01/2024

3.3.7.6 Additional laboratory studies and clinic visits will be performed if clinically indicated.

- 3.3.7.7 FDG-PET scan and/or DW-MRI will be performed on patients at baseline, during cycles 1-8 if patient obtains CR or at the end of cycle 8 if no CR is achieved, during cycles 9-20 if patient obtains CR or at the end of cycle 20 if no CR is achieved, and during cycle 21 and beyond if patient obtains CR or at treatment termination. During extension phase lenalidomide, FDG-PET scans and/or DW-MRIs are optional for those patients that are MRD negative at the end of cycle 8 regardless of response. At PI discretion, patient may be asked to have an additional PET-CT and/or DW-MRI at progression.
- 3.3.7.8 During lenalidomide extension phases I and II, FCBP patients will still be required to have pregnancy testing as outlined in **APPENDIX B**. Local treating physicians will be required to submit results to NIH clinical center for review.

Version Date: 01/01/2024

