a. Routine tests include CBC with differential, reticulocyte count, Acute Care (sodium, potassium, chloride, CO2, glucose, BUN, creatinine), Mineral (serum calcium, phosphate, magnesium and albumin) and Hepatic (alkaline phosphatase, ALT, AST, total and direct bilirubin) Panels, uric acid, eGFR determination, and LDH. NOTE: PT and PTT will only be performed at baseline.

- b. Viral studies include Hep B surface antigen and Hep C antibody. If Hep C antibody positive, Hep C RNA PCR will be performed
- c. Pregnancy tests (urine or serum) for females of childbearing potential. A female of childbearing potential (FCBP) is a sexually mature female who: 1) has not undergone a hysterectomy or bilateral oophorectomy; or 2) has not been naturally postmenopausal for at least 24 consecutive months (i.e., has had menses at any time in the preceding 24 consecutive months). During extension phase, FCBP patients will have pregnancy tests per footnote "e". Local treating physicians will be required to submit results to NIH Clinical Center for review.
- d. Pregnancy tests (urine or serum) must occur within 10 14 days and again within 24 hours prior to prescribing lenalidomide for Cycle 1 (prescriptions must be filled within 7 days).
- e. FCBP with regular or no menstruation must have a pregnancy test (serum or urine) weekly for the first 28 days and then every 28 days while on therapy (including breaks in therapy); at discontinuation of lenalidomide and at Day 28 post the last dose of lenalidomide. Females with irregular menstruation must have a pregnancy test (serum or urine) weekly for the first 28 days and then every 14 days while on therapy (including breaks in therapy), at discontinuation of lenalidomide and at Day 14 and Day 28 post the last dose of lenalidomide (see **APPENDIX B**).
- f. Myeloma tests include serum protein electrophoresis, serum immunofixation, urine electrophoresis, urine immunofixation, serum free light chains, quantitative immunoglobulins, beta-2 microglobulin and will be performed at baseline and Day 1 of each cycle. Subsequent serum immunofixation, urine immunofixation, and urine electrophoresis will only be performed on those patients clinically indicated.

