- 1. Urine for protein electrophoresis (UPEP) and immunofixation to assess for monoclonal protein in the urine (Bence-Jones proteinuria) at screening, day 1 of each cycle during cycles 1-8, day 1 of (or within 7 days prior to day 1) every third cycle during cycles 9-32, and at treatment termination. In patients whose measurable disease is best determined by measuring Bence- Jones protein quantification, a 24 hour UPEP will be performed at baseline, day 1 of each cycle 1-8, and day 1 (or within 7 days prior to day 1) of every third cycle during extension phase I and II. Otherwise, 24-hr UPEP Bence-Jones quantification will be estimated from random UPEP specimens performed at baseline, day 1 of each cycle 1-8, and day 1 (or within 7 days prior to day 1) of every third cycle during extension phase [46].
- m. FDG-PET scan will be performed on patients at baseline, during cycles 1-8 if patient achieves CR and/or at the end of cycle 8 if no CR is achieved, during cycles 9-20 (extended dosing phase I) if patient achieves CR and/or at the end of cycle 20 if no CR is achieved, and during cycles 21-32 (extended dosing phase II) if CR is achieved or at treatment termination. FDG-PET scan can be performed +/- 21 days of intended cycle day. For patients who are on extended dosing with lenalidomide and are found to be negative by immunohistochemistry and flow cytometry of the bone marrow (MRD negative), clearance of abnormal protein in blood and/or urine does not mandate a repeated bone marrow and the results will be interpreted as complete response. However, a bone marrow will be repeated at the discretion of investigator. Diffusion weighted MRI (DW-MRI) will also be performed at the discretion of the PI. DW-MRI will be performed by standard techniques in the NCI Molecular Imaging Program. In follow up, PET/CTs and DW-MRIs will be done approximately annually, if feasible (i.e., missed scans will not be considered protocol deviations). Note: DW-MRIs are optional after Cycle 8.
- n. Bone marrow biopsy and aspirate will be performed on patients at baseline, during cycles 1-8 if patient achieves CR or at the end of cycle 8 if no CR is achieved, during cycles 9-20 (extended dosing phase I) if patient achieves CR or at the end of cycle 20 if no CR is achieved, and during cycles 21-32 (extended dosing phase II) if CR is not achieved or at treatment termination. Bone marrow aspirate and biopsy can be performed +/- 21 days of intended cycle day.

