# • Complete Response (CR)

Negative immunofixation on the serum and urine and disappearance of any soft tissue plasmacytomas and  $\leq$ 5% plasma cells in bone marrow

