## • Relapse from CR

Any one or more of the following:

- Reappearance of serum or urine M-protein by immunofixation or electrophoresis. Appearance of monoclonal or oligoclonal bands that are different from original isotype may not be defined as "relapse from CR".
   Oftentimes, such bands may indicate fluctuations in immunological parameters that are not reflective of MM disease. In these situations, immunofixation and electrophoresis will be interpreted by the clinician before being labeled as "relapse".
- o Development of  $\geq 5\%$  plasma cells in the bone marrow

Version Date: 01/01/2024

o Appearance of any other sign of progression (i.e., new plasmacytoma, lytic bone lesion, hypercalcemia.

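### Immunofixation is discretionary in post-treatment follow-up although its reappearance defines relapse from CR; the CR and relapse marrow limits also overlap at exactly 5%

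*Combined protocol and SAP*

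**What the plan says.** **Endpoint definitions (section 6.3.2.1).** CR requires "Negative immunofixation on the serum and urine and disappearance of any soft tissue plasmacytomas", with ≤5% marrow plasma cells. MRD(-) CR is CR plus negative flow cytometry. Relapse from CR needs any one of several criteria. One is "Reappearance of serum or urine M-protein by immunofixation or electrophoresis"; another is development of ≥5% marrow plasma cells.

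**Serum schedule.** Section 3.3.7.3 puts serum immunofixation among the myeloma tests, with the timing "will be performed at baseline and Day 1 of each cycle and on Day 1 (or within 7 days prior to day 1) of every"; the interval in extension is three cycles. The next sentence is "Subsequent serum immunofixation will only be performed on those patients clinically indicated".

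**Urine schedule.** Section 3.3.7.4 has random urine electrophoresis and immunofixation "to be performed at baseline, day 1 of each cycle 1-8, and day 1(or within 7 days prior to day 1) of every third cycle" of extension. Calendar footnote l covers "Urine for protein electrophoresis (UPEP) and immunofixation to assess for monoclonal protein in the urine" and times it "at screening, day 1 of each cycle during cycles 1-8, day 1 of (or within 7 days prior to day 1) every third cycle" in cycles 9-32, plus treatment termination. Footnote f, which governs the calendar's myeloma-tests row, says instead: "Subsequent serum immunofixation, urine immunofixation, and urine electrophoresis will only be performed on those patients clinically indicated".

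**Follow-up.** As the calendar can be read, the follow-up column marks the myeloma-tests row, which is subject to footnote f. The urine row is blank there. Section 6.3 requires response assessments every 3-6 months in follow-up without listing the tests. Patients followed mainly outside are to supply response data at least yearly.

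**The concern.** Immunofixation can become positive while electrophoresis is still negative, and the plan counts that as relapse from CR. If the test is left to the clinician, with no stated trigger, such a relapse is found only when someone orders it.

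The endpoints at stake are those that end when CR is lost: duration of MRD(-) CR, the fraction with MRD(-) CR lasting at least one year (both secondary), and duration of best response in section 6.3.4, which ends at recurrent or progressive disease. The error runs one way: a test that is not done can delay or hide a relapse but cannot bring its date forward.

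The 5% marrow overlap is a separate fault in the classification rule. One marrow result can satisfy both the CR limit and a criterion for having lost CR.

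**Working it through.** **1. The two readings of *subsequent*, side by side.**

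| Period | After baseline | After the on-treatment schedule just listed |
|---|---|---|
| Serum, cycles 1-8 | Discretionary, against the preceding sentence | Scheduled each cycle |
| Serum, cycles 9-32 | Discretionary, against the preceding sentence | Scheduled every third cycle |
| Urine, cycles 1-32 | Footnote f conflicts with 3.3.7.4 and footnote l | Scheduled; the passages can stand together |
| Serum, follow-up | Discretionary | Discretionary |
| Urine, follow-up | Discretionary, no row entry | Discretionary, no row entry |

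The second reading is the more natural one, because it does not set each schedule against its own next sentence. The follow-up rows are the same under both.

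**2. Which endpoints depend on it.**
- *CR confirmation.* Section 6.3.1 calls for a 24-hour UPEP to confirm CR once serum and random urine are negative, including on immunofixation. The test is therefore expected when CR is declared.
- *Relapse from CR.* No equivalent instruction applies after CR is declared.
- *Duration of response, section 10.2.* It ends at progression or death. The PD definition has no immunofixation criterion; its serum limb needs a rise of at least 25% and at least 0.5 g/dL.
- *Duration of best response, section 6.3.4.* The word for recurrence lets relapse from CR in.
- *Duration of MRD(-) CR and the durable rate.* The plan gives no separate rule for their end. I assume that relapse from CR ends them.

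**3. When the one-year window leaves treatment** (nominal cycle lengths).
- Extension phase I: 12 × 28 = 336 days. Phases I and II: 24 × 28 = 672 days.
- MRD(-) CR first reached at the end of cycle 8, phase I only: 365 − 336 = 29 days of the window fall in follow-up.
- Same patient, both phases: 672 > 365, so the window closes on treatment.
- MRD(-) CR first reached at the end of cycle 20, both phases completed: 336 days of treatment remain, so again 29 days fall in follow-up.
- Early stopping lengthens the exposed part.

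For many patients the durable rate is therefore settled on treatment. Duration of MRD(-) CR stays exposed for everyone still in CR when treatment ends.

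**4. Size.**
- The plan's precision figure for the MRD(-) CR rate, as a yardstick: 1.96 × √(0.70 × 0.30 / 50) = 0.127, matching the stated ±12.7%. At 85%, 1.96 × √(0.85 × 0.15 / 50) = 0.099, matching ±9.9%. Neither changes. The plan gives no half-width for the durable rate.
- One patient wrongly counted as durable: 1/50 = 2 points. The number affected is not given; an assumed 1 to 5 patients gives 2 to 10 points.
- A test left out at a follow-up visit postpones the recorded relapse by at least one visit interval, but only if relapse has already occurred and shows on immunofixation alone. The interval is 3-6 months, and footnote q allows a further 6, so up to 6 + 6 = 12 months.

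**5. Marrow limits.** ≤5% and ≥5% share exactly one value, 5%. A patient moving from 3% to 5% still meets the CR limit and has also met a relapse criterion.

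**The case against.** The strongest reply is that *subsequent* means after the on-treatment schedule, so the passages agree and the gap is confined to follow-up. I accept that this is the more natural reading. The word is still undefined, and the follow-up gap remains.

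A reader might infer four stronger things that the documents do not support:
- *That immunofixation after baseline is done only when indicated, so CR and the primary endpoint are not reliably measured.* The preceding sentence of 3.3.7.3, section 3.3.7.4, footnote l and the CR confirmation step in 6.3.1 all point the other way.
- *That duration of response in section 10.2 is biased.* Its end event has no immunofixation component.
- *That relapse on treatment is recorded at least 84 days (3 × 28) late.* This needs the less natural reading, and a relapse that electrophoresis misses.
- *That the 2012-2014 and 2017-onward cohorts differ in ordering habits.* Nothing in the documents shows it.

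Other relapse criteria remain in force, and serum electrophoresis is among the myeloma tests in follow-up, so only immunofixation-only relapses are exposed. On marrow, *development of* may imply a rise, but the 3% to 5% example shows that this does not remove the overlap. The overlap will seldom decide a case: it concerns one value, and section 5.1.1 makes extension marrows optional for patients MRD negative at the end of cycle 8.

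Finally, the calendar notes that all participants had completed cycle 32 by February 2023, so changing on-treatment testing would help nobody. That stands, and it shapes the fix.

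**Conclusion.** The point holds for post-treatment follow-up. Sections 3.3.7.3 and 3.3.7.4 and footnotes f and l do not give one immunofixation schedule, and on every reading the test is discretionary once treatment ends. Immunofixation-only relapses may be dated late or missed. The effect can only lengthen duration of MRD(-) CR, duration of best response under section 6.3.4 and, for patients whose one-year window extends past treatment, the durable MRD(-) CR rate.

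The size is 2 points on the durable rate per patient of 50; how many patients are affected cannot be told from the documents. This assumes that relapse from CR ends MRD(-) CR and that 50 is the denominator. No effect on initial CR confirmation, the primary precision figures or duration of response under section 10.2 is shown.

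The 5% marrow overlap is a genuine but narrow contradiction.

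**What to change.** 1. Reconcile 3.3.7.3, 3.3.7.4 and footnotes f and l into one immunofixation schedule tied to the response assessments in section 6.3. For patients in CR with negative electrophoresis, run serum immunofixation on the serum already drawn at each follow-up visit, until relapse. Test urine where a sample is available; routine follow-up urine testing would need samples not now scheduled.
2. Make the CR and relapse-from-CR marrow limits mutually exclusive.
3. For data in hand, add a sensitivity analysis of MRD(-) CR duration and the durable rate that treats loss of CR as interval-censored between the last negative and first positive immunofixation. Censor patients with no documented relapse at their last negative immunofixation, and report how many are affected.

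The cost is one assay on existing serum for patients still followed, a little analysis work, and possibly slightly shorter durations. Where follow-up is at an outside facility, the result has to be requested and may not exist; the sensitivity analysis covers that case.

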## 3.4 STUDY CALENDAR

Test/Procedure			Induction Treatment q					ent q	End of			
	Screening	Baseline	Cycle 1			Cycle 2-8		Extended Treatment (Phases I and II) q		Treatment r and Follow-Up	Disease	
			Day 1	Day 8	Day 15	Day 22	Day 1	CR Achieved/ End of Cycle 8 l, m, n	Day 1 of every third cycle from cycle 9 and beyond p	Phase I-CR Achieved (Cycle 9-20)/ End of Cycle 20 and Phase II-CR achieved (Cycle 21-32)/ Treatment termination 1, m, n, p	Every 3-6 months j, m, q	Progression at any Time Point k
Medical Record Review	X										X	
H&P/Clinic Visit	X		X	X	X	X	X		X			
ECOG	X						X		X			
Informed Consent	X											
Routine Labs a	2	K	X	X	X	X	X		X		X	
Urine for UPEP and IFE 	xl		X				x l	$\mathbf{x}^{\mathrm{l}}$	$\mathbf{x}^{\mathrm{l}}$	x l		
Viral Studies b	Х											
Register for RevAssist		X										
Pregnancy Test c	xc		x d	Xe	xe	xe	xc		x c,e	X e	xe	
Myeloma tests f	X						X		X	Xº	X	
Research Blood/Urine *		X		X	X		X	X	X	X	X	X
Bone Marrow/Aspirate	Х	g						x i, n		X i, n	X i	X
Skeletal Survey	X											
FDG PET-CT		X						X m		X m	X	X
MRI of spine	X s											
Diffusion Weighted MRI		X						X m		X m	X m	X m
Echocardiogram, BNP and Troponin		X										
Adverse Events			X									
12 lead EKG	Х											

NOTE: All assessments are pre-dose on the day indicated, unless otherwise described below. After initiation of treatment, variations of +/- 3-14 days of scheduled visits are permitted, as noted (see also footnote q). For patients who choose to undergo stem cell harvest, next cycle may be delayed for up to 5 weeks. Refer to Section 5.1 for specific details on research samples and imaging correlates to be collected. \*See Section 5, Correlative Studies for Research, for additional information on the research blood, urine, and bone marrow sampling. Note, that any missed research blood/urine tests or surveys will not be considered protocol deviations.

*Version Date:* 01/01/2024

a. Routine tests include CBC with differential, reticulocyte count, Acute Care (sodium, potassium, chloride, CO2, glucose, BUN, creatinine), Mineral (serum calcium, phosphate, magnesium and albumin) and Hepatic (alkaline phosphatase, ALT, AST, total and direct bilirubin) Panels, uric acid, eGFR determination, and LDH. NOTE: PT and PTT will only be performed at baseline.

- b. Viral studies include Hep B surface antigen and Hep C antibody. If Hep C antibody positive, Hep C RNA PCR will be performed
- c. Pregnancy tests (urine or serum) for females of childbearing potential. A female of childbearing potential (FCBP) is a sexually mature female who: 1) has not undergone a hysterectomy or bilateral oophorectomy; or 2) has not been naturally postmenopausal for at least 24 consecutive months (i.e., has had menses at any time in the preceding 24 consecutive months). During extension phase, FCBP patients will have pregnancy tests per footnote "e". Local treating physicians will be required to submit results to NIH Clinical Center for review.
- d. Pregnancy tests (urine or serum) must occur within 10 14 days and again within 24 hours prior to prescribing lenalidomide for Cycle 1 (prescriptions must be filled within 7 days).
- e. FCBP with regular or no menstruation must have a pregnancy test (serum or urine) weekly for the first 28 days and then every 28 days while on therapy (including breaks in therapy); at discontinuation of lenalidomide and at Day 28 post the last dose of lenalidomide. Females with irregular menstruation must have a pregnancy test (serum or urine) weekly for the first 28 days and then every 14 days while on therapy (including breaks in therapy), at discontinuation of lenalidomide and at Day 14 and Day 28 post the last dose of lenalidomide (see **APPENDIX B**).
- f. Myeloma tests include serum protein electrophoresis, serum immunofixation, urine electrophoresis, urine immunofixation, serum free light chains, quantitative immunoglobulins, beta-2 microglobulin and will be performed at baseline and Day 1 of each cycle. Subsequent serum immunofixation, urine immunofixation, and urine electrophoresis will only be performed on those patients clinically indicated.
- g. Baseline bone marrow aspiration and biopsy will be sent to Dept. of Pathology, flow cytometry, FISH/cytogenetics, CD 138 sorting/GEP/storage ([name] Lab) and heavy/light chain immunoglobulin rearrangement (optional) and/or NRAS/KRAS mutations in Molecular Pathology (optional). For screening eligibility purposes, an outside bone marrow may be used in which case a baseline at the NIH will also be performed. **Note:** As of February 6, 2023, all participants have completed the maintainance phase (C32) thus bone marrow and peripheral blood research samples will be sent to [name]'s lab on a case to case basis.
- h. FOOTNOTE NO LONGER APPLIES/DELETED IN AMENDMENT M (version date 07/20/2018). PREVIOUS TEXT: Optional Cycle 1 Day 2 bone marrow aspirate alone sent for CD138 sorting (GEP studies and microenvironment studies). NOTE: This no longer in effect with Amendment H (version date 06/30/2017).
- i. Bone marrow aspirate and biopsy can be performed +/- 21 days of intended cycle day. Bone marrow aspirate and biopsy will be sent to Hematology Section, Department of Lab Medicine (DLM), flow cytometry (bone marrow immunophenotyping of plasma cells), CD 138 sorting/GEP/storage, and +/- heavy/light chain immunoglobulin rearrangement and/or NRAS/KRAS mutations in Molecular Pathology (optional). In follow up period, PET/CTs will be done approximately annually.
- j. At minimum, follow-up will be every 3-6 months until progression of disease, or death. Patients may be followed at more frequent time intervals if clinically indicated, i.e. following post-therapy toxicity. Patients who have progressive disease while on study will be followed with restaging scans and laboratory tests as clinically indicated. Patients who are taken off treatment will continue to be followed for survival by phone or clinic visit. Patients who finish all 32 cycles of treatment will be followed at least every 6 months by clinic visit with laboratory evaluation and by bone marrow biopsy yearly at the discretion of the investigator. Of note, patients who do not progress, but decide to

*Version Date:* 01/01/2024

continue or resume therapy at an outside facility, may be followed by clinical and laboratory examination every 3-6 months. Alternatively, this data may be captured by investigator-patient or investigator-physician phone or email communication if the required examinations have been performed at the outside facility.

- k. At disease progression, marrow and FDG-PET/CT are optional.
- 1. Urine for protein electrophoresis (UPEP) and immunofixation to assess for monoclonal protein in the urine (Bence-Jones proteinuria) at screening, day 1 of each cycle during cycles 1-8, day 1 of (or within 7 days prior to day 1) every third cycle during cycles 9-32, and at treatment termination. In patients whose measurable disease is best determined by measuring Bence- Jones protein quantification, a 24 hour UPEP will be performed at baseline, day 1 of each cycle 1-8, and day 1 (or within 7 days prior to day 1) of every third cycle during extension phase I and II. Otherwise, 24-hr UPEP Bence-Jones quantification will be estimated from random UPEP specimens performed at baseline, day 1 of each cycle 1-8, and day 1 (or within 7 days prior to day 1) of every third cycle during extension phase [46].
- m. FDG-PET scan will be performed on patients at baseline, during cycles 1-8 if patient achieves CR and/or at the end of cycle 8 if no CR is achieved, during cycles 9-20 (extended dosing phase I) if patient achieves CR and/or at the end of cycle 20 if no CR is achieved, and during cycles 21-32 (extended dosing phase II) if CR is achieved or at treatment termination. FDG-PET scan can be performed +/- 21 days of intended cycle day. For patients who are on extended dosing with lenalidomide and are found to be negative by immunohistochemistry and flow cytometry of the bone marrow (MRD negative), clearance of abnormal protein in blood and/or urine does not mandate a repeated bone marrow and the results will be interpreted as complete response. However, a bone marrow will be repeated at the discretion of investigator. Diffusion weighted MRI (DW-MRI) will also be performed at the discretion of the PI. DW-MRI will be performed by standard techniques in the NCI Molecular Imaging Program. In follow up, PET/CTs and DW-MRIs will be done approximately annually, if feasible (i.e., missed scans will not be considered protocol deviations). Note: DW-MRIs are optional after Cycle 8.
- n. Bone marrow biopsy and aspirate will be performed on patients at baseline, during cycles 1-8 if patient achieves CR or at the end of cycle 8 if no CR is achieved, during cycles 9-20 (extended dosing phase I) if patient achieves CR or at the end of cycle 20 if no CR is achieved, and during cycles 21-32 (extended dosing phase II) if CR is not achieved or at treatment termination. Bone marrow aspirate and biopsy can be performed +/- 21 days of intended cycle day.
- o. Repeat myeloma tests at treatment termination.
- p. Within 7 days prior to D1 of each cycle.
- q. After initiation of treatment, visits may be adjusted per PI discretion for logistical or administrative reasons (e.g. holidays, bad weather, etc.); this may include skipped doses of lenalidomide. For cycles 2-8, the preferred adjustment is -1/+3-day with no more than 2 missed doses of lenalidomide. For cycles 9-forward, the preferred adjustment is -1/+7 days. For follow-up period may be adjusted from every 3-6 months to up to 6 months (+6 months) at the discretion of the PI
- r. End of treatment visit will occur approximately 30 days (+/- 7 days) after the last dose of study drug. If the patient cannot return to the Clinical Center for this visit, a request will be made to collect required clinical labs (specify as needed) from a local physician or laboratory. If this is not possible, patients may be assessed by telephone for symptoms.
- s. At the discretion of the Principal Investigator, PET/CT may replace MRI in patients who have a contraindication to MRI.

Version Date: 01/01/2024

